5.5.3 Regained Capacity Consent

If the original process involved anyone other than the participant, and if required by local standards, consent will be sought for the remaining procedures from the participant once they are deemed to have regained capacity. Site staff will make ongoing efforts until: (1) regained capacity consent is obtained from participant, (2) death, or (3) completion of the Day 90 assessment.

5.5.4 Amendment of the ICF

In the event that new information is available and the ICF is amended, and if required by local IRBs, participants must be re-consented to the most current version of the ICF(s) during their participation in the trial. A copy of each ICF must be provided to the participant or the participant's legally authorized representative.

Note: Electronic consent tools may be used for initial and regained capacity consent, as permitted under applicable laws and regulations and the IRBs.

5.5.5 Physical Examinations

To support the assessment of inclusion and exclusion criteria and medical history, a stroke focused physical examination at baseline will include, at a minimum, assessments of the Neurological, Cardiovascular, Respiratory, Genitourinary, and Gastrointestinal systems. Investigators should pay special attention to clinical signs related to previous strokes. Additionally, physical examinations will be conducted every 8-12 hours during the treatment phase to assess any signs of fluid overload or worsening of any clinical symptoms. Results taken from standard of care assessment/timepoints may be used.

6 STUDY INTERVENTIONS and CONCOMITANT THERAPY

6.1 Study Intervention Administration

RNS60 is produced using 0.9% sodium chloride for injection and medical grade oxygen. It is supplied in single-use IV bags and contains no preservatives. RNS60 has been extensively tested in preclinical toxicological studies and has shown little attributable side effects to date. In addition, RNS60 was well tolerated in three Phase I human safety studies, one after IV administration and two after inhalation, and in other Phase I and Phase II studies, including one in multiple sclerosis and one in ALS patients¹⁴. More information can be found in the Investigator's Brochure.

RNS60 IV bags are to remain **Redacted**

RNS60 **Redacted**

Table 6-1: Study Interventions

	RNS60	Placebo
Test Product Name	RNS60	Placebo
Type	Drug	Drug
Dose Formulation	Sterile fluid for IV infusion	Sterile fluid for IV infusion
Dosage Level(s)	0.5 mL/kg/h and 1 mL/kg/h	1 mL/kg/h
Route of Administration	IV Infusion	IV Infusion
Use	Investigational	Placebo
Sourcing	Provided by the sponsor	Provided by the sponsor
Packaging and Labeling	Study drug will be provided in 375-mL IV bags	Study drug will be provided in 375-mL IV bags Redacted

6.2 Preparation / Handling / Storage / Accountability

Only participants enrolled in the trial may receive study drug and only authorized site staff may supply or administer study drug. Study drug dosing will be carried out by, or under the supervision of, the investigator who is supervising the care of the participant for the planned or ongoing endovascular reperfusion procedure.

As soon as the participant is deemed eligible for the trial, the investigator (or delegate) will log into the central randomization website to receive the assigned bag number.

Dose timing starts at the time of infusion onset. Study drug is intended to be administered as soon as possible after randomization (i.e., <30 minutes) and must be started prior to arterial access closure.

Study drug will be provided in a **Redacted** will contain 375 mL of study drug for single use only.

Redacted**Redacted**

Research site staff will inform the Investigational Pharmacy about local inventory so that the pharmacy can prepare and have correct bags (RNS60 or placebo) on time to study staff.

6.2.1 Storage and Accountability

Study drug must be stored in a secure, temperature controlled (2 to 8°C), and monitored (manual or automated) area in accordance with the labeled storage conditions with access limited to the investigator and authorized site staff. Temperatures will be monitored using a device that can continuously monitor and record temperature readings.

The drug supply will have access limited to the investigational pharmacy staff and those directly involved in the study.

The investigator and investigational pharmacist are responsible for study drug accountability, reconciliation, and record maintenance (i.e., receipt, reconciliation, and final disposition records). Any expired, lost, damaged or out-of-specification study drug must be properly documented and reported to the sponsor.

6.2.2 Disposition of Study Drug Supplies

Following IV administration, any remaining fluid may be disposed of in any normal drain. Empty bags will not be retained. Used bags will be disposed of on site. Drug accountability will be captured by study staff and pharmacy staff using Drug Accountability Logs and the CRO's investigational product management system to record bags used (using Bag IDs). Any unused IV bags will be destroyed/disposed of or returned to sponsor at the conclusion of the study.

6.3 Measures to Minimize Imbalance: Block Urn Randomization and Blinding

All patients will be centrally assigned to a randomized study intervention (i.e. RNS60 0.5 mL/kg/h, RNS60 1mL/kg/h, or placebo 1 mL/kg/h) using block urn randomization tables (8 urns). The randomization table will be set for up to 100 people per urn to ensure no urn can be filled prior to enrollment completion. Each site will have their own randomization table.

Treatment allocation will be assigned using 1:1:1 randomization (RNS60 0.5 mL/kg/h, RNS60 1 mL/kg/h, or placebo 1 mL/kg/h). Randomized allocation will be fully concealed by having allocations based upon random assignment and blinded by the use of visually identical appearing RNS60 and placebo infusion bags. All infusion bags will have a unique number.

The purpose of using block urn randomization is to minimize the possibility of imbalance of treatment assignment by age, NIHSS score, and ASPECTS due to the small sample size.

All participants, investigators, their clinical staff, local and central laboratories, the clinical coordinating center, the data management group, and the sponsor staff and delegates will be blinded to the randomization codes.

6.3.1 Appendix 1 Block Urn Randomization

Because of the small sample size distributed among three arms, imbalance of treatment assignment across important baseline factors should be minimized. Block urn randomization provides consistent imbalance control but provides greater allocation randomness compared with permuted block design¹⁵. Block urn designs use blocking of balls with an active urn and inactive urn. A ball is randomly selected from the active urn (treatment allocation) and then placed in the inactive urn; this process is repeated until a minimum balance is achieved in the inactive urn at which point these balls are replaced in the active urn while the other balls are left in the inactive urn. This process is repeated until the last patient is randomized. Block urn randomization has been used in other stroke trials¹⁶⁻¹⁸.

6.3.2 Procedure for Breaking the Randomization Code

In case of an emergency, the investigator has the sole responsibility for determining whether the unblinding of a participant's intervention assignment is warranted. Participant safety must always be the first consideration in making such a determination. If the investigator decides that unblinding is warranted, the investigator should make every effort to contact the sponsor prior to unblinding a participant's intervention assignment unless this could delay emergency treatment of the participant. If a participant's intervention assignment is unblinded, the sponsor must be notified within 24 hours after breaking the blind[†]. The date and the reason why the blind was broken must be recorded in the source documentation as applicable.

To maintain the overall quality and legitimacy of the clinical trial, code breaks should occur only in exceptional circumstances when knowledge of the actual treatment is absolutely essential for further management of the patient to ensure their safety and well-being.

In case of an emergency, a rapid unblinding procedure is available to investigators. The investigator will contact the randomization provider to request unblinding of the specific participant. The randomization provider will respond in writing to the investigator only with the unblinded participant treatment allocation.

Only the investigator requesting the unblinding will receive the unblinding information. The investigator is requested to maintain the blind as far as possible. The actual treatment allocation should not be disclosed to the participant and/or other site personnel unless, in the judgment of the

[†] In cases where a participant was unblinded on a Friday, where possible the investigator will aim to send the notification prior to the weekend. If not possible, or if the unblinding occurs on a weekend or a holiday, notification will be sent on the first business day after the event.

investigator, this information is required for the participant's safety. The actual treatment allocation must not be disclosed to study personnel on site not involved in the participant's medical care, to monitors or the sponsor.

In order to fulfill expedited regulatory reporting requirements, the sponsor may be required to unblind the participant if the SAE meets the criteria for reporting to health authorities. The sponsor's independent third party (CRO) will initiate the request that the participant's treatment group be unblinded. In this case, the code will be broken only for the participant(s) in question. The information resulting from code-breaking (i.e., the participant's treatment allocation) will not be communicated to either the investigator or the sponsor, except as needed for determination of causality of a reportable SAE.

Otherwise, randomization data will be kept strictly confidential, accessible only to authorized persons, until the time of unblinding after database lock at the time of interim analysis and at end of the study (Day 90).

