8.2.4 Regulatory Reporting Requirements for SAEs

Prompt notification by the investigator to the sponsor of an SAE is essential so that legal obligations and ethical responsibilities towards the safety of participants and the safety evaluation of the study drug under clinical investigation are met.

The sponsor has a legal responsibility to notify the FDA about the safety of a study intervention under clinical investigation. The sponsor will comply with regulatory requirements relating to safety reporting to the regulatory authority, IRBs, and investigators.

- ***Initial reporting:*** IND application sponsor must report any suspected adverse reaction or adverse reaction to study treatment that is both serious and unexpected.

Suspected unexpected serious adverse reactions (SUSARs) and observations from animal studies suggesting significant risk to human subjects must be reported to FDA as soon as possible but no later than within **15 calendar days** following the sponsor's initial receipt of the information.

Unexpected fatal or life-threatening suspected adverse reactions represent especially important safety information and must be reported to FDA as soon as possible but no later than **7 calendar days** following the sponsor's initial receipt of the information.

- **Follow-up reporting:** Any relevant additional information obtained by the sponsor that pertains to a previously submitted IND safety report must be submitted as a Follow-up IND Safety Report. Such report should be submitted without delay, as soon as the information is available but no later than 15 calendar days after the sponsor receives the information

Investigator safety reports must be prepared by the sponsor for SUSARs according to local regulatory requirements and sponsor policy and forwarded to investigators as necessary.

The Sponsor will notify the Investigators in writing of the occurrence of any reportable SAEs. The Investigators will be responsible for informing their local IRBs of any reportable SAEs as per their local requirements.

An investigator who receives an investigator safety report describing an SAE or other specific safety information (e.g., summary or listing of SAEs) from the sponsor will review and then file it along with the Investigator's Brochure and will notify the IRB, if appropriate according to local requirements.

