- The investigator will also consult the Investigator’s Brochure (IB) and/or Product Information, for marketed products, in his/her assessment.
- For each AE/SAE, the investigator **must** document in the medical notes that he/she has reviewed the AE/SAE and has provided an assessment of causality.
- There may be situations in which an SAE has occurred and the investigator has minimal information to include in the initial report to the sponsor. However, it is very important that the investigator always make an assessment of causality for every event before the initial transmission of the SAE data to the sponsor.
- The investigator may change his/her opinion of causality in light of follow-up information and send a SAE follow-up report with the updated causality assessment.
- The causality assessment is one of the criteria used when determining regulatory reporting requirements.

AE Causality/ Relationship

Related	A clinical event, including laboratory test abnormality, where there is a “reasonable possibility” that the SAE was caused by the study drug, meaning that there is evidence or arguments to suggest a causal relationship.
Possibly:	A clinical event, including laboratory test abnormality, with a reasonable time sequence to drug administration, but which could also be explained by concurrent disease or other drugs or chemicals. Information on drug withdrawal may be lacking or unclear.
Unrelated:	This category is applicable to AEs which are judged to be clearly and incontrovertibly due to extraneous causes (diseases, environment, etc.) and do not meet the criteria for drug relationship listed for the above-mentioned conditions.

Follow-up of AEs and SAEs

- The investigator is obligated to perform or arrange for the conduct of supplemental measurements and/or evaluations as medically indicated or as requested by the sponsor to elucidate the nature and/or causality of the AE or SAE as fully as possible. This may include additional laboratory tests or investigations, histopathological examinations, or consultation with other health care professionals.
- If a participant dies during participation in the study the investigator may be requested by the sponsor to provide the sponsor with a copy of any post-mortem findings including histopathology.
- New or updated information will be recorded in the originally completed CRF.
- The investigator will submit any updated SAE data to the sponsor within 24 hours of receipt of the information.

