All participants, investigators, their clinical staff, local laboratories, study personnel, the data management group, and the sponsor staff and delegates will be blinded to the randomization codes and study drug assignment. All study personnel (Contract Research Organization (CRO) and Sponsor and sites) will remain blinded to this data until database lock, at minimum. In the event of emergency unblinding due to participant safety, the Investigator may request unblinding of that participant only. Processes and procedures for unblinding will be accordance with the study protocol, Data Management Plan, Safety Management Plan, and any applicable CRO or Sponsor Standard Operating Procedures.

2.2.3 *Study Drug*

RNS60 is [REDACTED]

[REDACTED] RNS60 has demonstrated exceptional safety in rodent and non-human primate toxicity studies. Additionally, RNS60 has demonstrated significant efficacy in a non-human primate model of acute ischemic stroke without any indications of adverse effects. In all clinical studies to date, RNS60 has been well tolerated. In this study, infusion will begin prior to the completion of the endovascular revascularization procedure (defined as the time of arterial access closure) and complete 48h after the infusion is initiated.

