3.5.1 Adverse Events (AEs)

An AE is defined as any untoward medical occurrence in a subject or clinical investigation participant administered a pharmaceutical product and which does not necessarily have to have a causal relationship with this treatment.

An AE can therefore be any unfavorable and unintended sign (including an abnormal laboratory finding, for example), symptom or disease temporally associated with the use of a medicinal product, whether or not considered related to the medicinal product. AEs will be captured from the start of study drug infusion through study completion (Day 90). All AEs will be coded to system organ class and preferred term using MedDRA version 24.0. A medical review of the coding reports will be performed prior to database lock. Treatment-emergent adverse events (TEAEs) are defined as AEs that start after the study drug infusion.

The investigator will grade the intensity of the AE as mild, moderate, or severe.

The relationship of an AE to study drug will be assessed as related, possibly related, or unrelated.

An overview of AEs will be provided including counts and percentages of subjects (and event counts) with the following:

- Any TEAEs (overall and by maximum severity)
- Any study drug related TEAEs (overall and by maximum severity)
- Any SAEs
- Any treatment-emergent serious AEs (TESAEs)
- Any study drug related TESAEs
- Any TEAEs leading to discontinuation of study drug infusion
- Any AEs leading to death
- TEAE occurrence by Month (Day 0-Day 7, Day 8 – Day 14, Day 15 – Day 21, Day 22 – Day 30, Day 31-Day 60, and Day 61-Day 90)

Counts and percentages of subjects (and event counts) will also be presented by system organ class and preferred term for each of the categories in the overview. If more than one event occurs with the same preferred term for the same subject, the subject will be counted only once for that preferred term using the most severe occurrence for the summary by severity. The number of events will be presented for overall category of TEAE and for each system organ class and preferred term. The number of events will not be presented for each category of maximum severity. AE listings will include the following information:

- Subject ID
- Adverse event term
- Adverse event preferred term
- System Organ Class
- Start date
- Outcome
- End date
- Relationship to study drug
- Action taken with study drug

- Severity
- SAE Criteria

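### Protocol 6.3.2 lets the allocation be disclosed to judge causality of a reportable SAE, so the descriptive drug-related event rows can contain calls made with the arm known

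*Protocol*

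**What the plan says.** Protocol 6.3.2 provides for a regulatory code break: "the sponsor may be required to unblind the participant if the SAE meets the criteria for reporting to health authorities". An independent third party (the CRO) starts the request, and only the participant concerned is unblinded. The result "will not be communicated to either the investigator or the sponsor, except as needed for determination of causality of a reportable SAE".

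Three other parts of the protocol bear on this exception:

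- Section 8.2.4 defines what is reportable: the sponsor "must report any suspected adverse reaction or adverse reaction to study treatment that is both serious and unexpected".
- Section 10.3.2 tells the investigator to "always make an assessment of causality for every event before the initial transmission of the SAE data to the sponsor".
- Section 10.3.2 also allows revision: "The investigator may change his/her opinion of causality in light of follow-up information and send a SAE follow-up report with the updated causality assessment". New information goes into the CRF record first completed.

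In the SAP, section 3.5.1 lists "Any study drug related TESAEs" among the overview rows, beside drug-related TEAEs, all SAEs and all TESAEs. SAP 2.2.2 says that CRO, sponsor and site personnel "will remain blinded to this data until database lock, at minimum". It names emergency unblinding requested by the investigator as the exception, and then refers unblinding procedures to the protocol and to other plans.

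**The concern.** Relatedness is a judgement, and in a blinded trial its value for comparing arms depends on its being made without knowledge of the arm. The exception discloses the arm for the very purpose of making that judgement. An investigator who learns that a participant received placebo has a reason to downgrade the call. One who learns that it was RNS60 has a reason to keep or raise it. If such revisions reach the analysis, the drug-related rows can differ between arms because of disclosure and not because of the drug.

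High-dose RNS60 and placebo run at the same infusion rate, so the infusion rate does not give away the arm in that comparison. SAP 2.2.2 concedes that staff involved in the infusion might recognise the low-dose arm. The exception can reveal the arm in the comparison that is otherwise best masked. It can do so while the participant is still being followed to Day 90 and later events still have to be judged.

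**Working it through.** The documents give no sample-size, power or event figure for this point, so there is nothing to reproduce. The check is the order of events, then which outputs use causality, then a scale.

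**1. Order of events for one reportable SAE**

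| Step | Source | Arm known to investigator or sponsor? |
|---|---|---|
| Investigator assesses causality before first transmission | Protocol 10.3.2 | Normally no |
| SAE is found serious, unexpected and a suspected reaction, hence reportable | Protocol 8.2.4 | Normally no |
| CRO requests the code break | Protocol 6.3.2 | Not by default |
| Allocation is released to the investigator or sponsor if needed for causality | Protocol 6.3.2 | Yes, under the exception |
| Causality may be revised and the CRF record updated | Protocol 10.3.2 | Possibly |
| Related TEAEs and TESAEs are tabulated by arm | SAP 3.5.1 | Depends on which call is used |

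Suspicion comes before reportability, and a causality call comes before transmission. At the fourth step a usable judgement therefore already exists, and the exception adds only the chance to revise it with the arm known. Neither document freezes the earlier call, requires revisions to be blinded, or names the call to be analysed.

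**2. Which outputs use causality**

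- Primary safety endpoints (SAP 2.3.1 and 3.4.1): SAEs whatever their cause, and 90-day mortality. Not affected.
- Fisher's exact tests (Protocol 9.3.3): SAEs, SAEs resulting in death, AEs, and discontinuations due to AEs. Not affected.
- Drug-related TEAE and TESAE rows, with their breakdowns by system organ class and preferred term (SAP 3.5.1). Affected; no test is planned for them.

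**3. Scale per reclassified participant**

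Inputs: 100 participants (SAP 2.2.4), allocated 1:1:1 (SAP 2.2.1).

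- Arm size: 100 / 3 = 33.3, taken as 33.
- One participant: 1 / 33 = 3.0 percentage points.
- Two: 2 / 33 = 6.1 points. Three: 3 / 33 = 9.1 points.

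How many participants would be reclassified is an assumption; the documents do not say.

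**4. A rough guide to exposure**

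Protocol 2.1.5 reports one possibly related SAE across three disease trials of 16, 148 and 10 patients.

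- 16 + 148 + 10 = 174; 1 / 174 = 0.57%.
- Expected in an arm of 33: 33 / 174 = 0.19 events.
- Expected in 100 participants: 100 / 174 = 0.57 events.

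This is a guide only. Those trials were in ALS and multiple sclerosis, and one was still ongoing. Acute stroke patients after thrombectomy may have more SAEs that someone suspects, while only unexpected ones are reportable. On this guide the likely number of reclassified participants is zero or one per arm.

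**The case against.** The strongest case on the other side is that the route is narrow and the consequence small. Non-disclosure is the default, the request comes from a third party, and one participant is unblinded at a time. Only SAEs that are serious, unexpected and already suspected are exposed. Fluid overload is named as the major possible risk in Protocol 2.3.1, so it is probably not unexpected, although the Investigator's Brochure decides that and is not available here. Revision is tied to follow-up information, and no text says that an unblinded call replaces the blinded one. All of this stands and limits the size. It does not close the route, because nothing prevents a revision after disclosure and nothing tells the programmer which call to use.

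Three stronger readings are tempting, and the documents do not support them.

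- A reader might infer that the primary SAE comparison is biased. It is not: neither primary endpoint uses causality.
- A reader might infer that every related event on placebo would become unrelated once the arm is known. With an assumed 3 of 33 on placebo and 6 of 67 on RNS60 (9.1% and 9.0%), that would create a 9-point excess on drug. But the placebo is saline at up to 130 mL/h for 48 hours. Protocol 6.6 treats that volume as a possible challenge, and Table 6-1 lists placebo as a study intervention of type drug. A placebo event can still be called related. The 9% is also assumed, against about 0.6% in Protocol 2.1.5.
- A reader might infer a flat contradiction with the SAP's statement that staff stay blinded to database lock. The two texts pull apart, but SAP 2.2.2 refers unblinding procedures back to the protocol, so this is tension and not a clean conflict.

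**Conclusion.** The concern holds as a limited one. A stated rule in Protocol 6.3.2 permits disclosure of the arm for causality assessment when a normally blinded call already exists. With revision allowed and no analysis rule in SAP 3.5.1, calls made with the arm known can enter the drug-related TEAE and TESAE rows. Those rows are descriptive.

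The size is about 3 percentage points in an arm for each reclassified participant, with 33 per arm. The number of such participants is not given and is probably small. The direction is not certain either, because the placebo is itself a volume load.

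The conclusion assumes that the tables are built from the current CRF value of causality, which the SAP neither states nor excludes, and that no other plan freezes the blinded call. The Safety Management Plan and Data Management Plan were not available to check this.

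**What to change.** **SAP 3.5.1.** State that the related TEAE and TESAE tables use the last causality recorded before any unblinding of that participant, and that later changes are listed separately. Events that start after a participant's unblinding have no such call; flag them in the listing and state how they are counted. This change alone removes the bias from revised calls in the tables. It needs the dated history of the causality field and the date of any code break, so data management should confirm that both can be retrieved.

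**Protocol 6.3.2.** Remove the causality exception, or limit it to the independent safety function that files the report. Add that investigator and sponsor causality is recorded before the regulatory code break. The third party is already in place, and expedited reporting is not impeded. Emergency unblinding for patient care stays as it is.

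The cost is one or two SAP sentences and a short protocol amendment, with no new data collection. The amendment needs IRB approval before implementation (Protocol 10.1.1). If that is not practical, the SAP change should go ahead by itself.
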